Acceptance Commitment Therapy (ACT): The ACT behavioral intervention includes discussing one's pain experience with a trained therapist and may make participants feel emotionally uncomfortable. These risks are minimal and are sometimes part of the therapeutic process. To reduce the disabling effects of depression, fear or other feelings, one may need to first recognize these before identifying healthy goals for improvement. Participants will meet with an assigned therapist four times and will be able to contact them at any time by email. The therapist will thoroughly explain treatment and what to expect. They will provide ongoing support over the course of treatment and, if applicable, will monitor the participant for worsening of depression or anxiety symptoms. Study participants may also reach out to study staff with any questions or concerns throughout the course of the study.

Duloxetine: Duloxetine will be administered with daily doses ranging from 30mg to 60mg. Participants will begin with 30 mg and may increase to 60 mg after seven days, if no or only mild side effects are experienced. Participants will be warned about the most common side effects with this drug, which include nausea, vomiting, nausea, dry mouth, constipation, diarrhea, fatigue, and difficulty sleeping. All of these side effects are thought to be less common with slow gradual dose escalation, and many (especially gastrointestinal intolerance) typically get better over time. The most serious adverse effect associated with duloxetine is the increased risk of suicidality with initiation, especially in individuals under age 25. Participants on duloxetine (of all ages) will be monitored appropriately for clinical worsening, suicidality, or unusual changes in behavior. Participants reporting a history of bipolar disorder, manic episodes, or suicide attempts and participants who are currently breastfeeding will not be eligible for participation in the Duloxetine intervention.

Enhanced Self Care (ESC): The ESC intervention is an educational and self-care digital intervention. Risks are minimal.

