otherwise eligible for the study will be allowed to participate in the study but will not be randomized to the intervention for which they have a contraindication. In Sections 10.1 (Acceptance Commitment Therapy), 10.2 (Duloxetine), 10.3 (Enhanced Self Care), and 10.4 (Evidence-Based Exercise and Manual Therapy) specific details regarding risk assessment and mitigation are given for each study intervention.

Participants will be advised that they should contact study staff regarding any side effects or unexpected adverse events that occur while enrolled in the study. Prior to the start of a new study intervention, participants will be informed that if they are unable to tolerate the intervention, they are permitted to cease the intervention. Specifically for duloxetine, participants will be instructed on how to safely taper off the medication. In addition, study staff will conduct a phone call assessment with all participants approximately midway into each of the two intervention periods to evaluate pain-related outcomes as well as to ascertain how well the participant is tolerating their current study intervention(s). Participants who indicate they are unable to tolerate the intervention will be safely transitioned off their current intervention but, if in intervention period one, will be allowed to be randomized to a new intervention in the second study period. Additionally, all participants will be assessed for unexpected and adverse events 4 weeks after the end of the second intervention period (i.e., after completion of all study treatment).

Acceptance Commitment Therapy: Participants will interact with their therapist at least weekly, and the therapist will provide support as well as monitor for worsening of depression or anxiety symptoms including suicidal ideation. Participants will be encouraged to contact study staff with questions or concerns throughout the course of the study.

Duloxetine: Participants on duloxetine will be monitored appropriately for clinical worsening, suicidality, or unusual changes in behavior. Participants may be referred for appropriate treatment including emergency services if required. Participation can also be discontinued if there is active suicidal ideation.

Enhanced Self Care: The ESC intervention is an educational and self-care digital intervention. Risks are minimal; therefore, no intervention-specific risk mitigation is planned.

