^{*} Patients initially randomized to ESC with 12-week PGIC scores of 3-7 will be randomized to augmentation and not switching.

Table 10.1 provides a list of all possible augmentations (combinations of the initial treatment with a second study intervention) and treatment switches for each of the initial treatment assignments. This randomization will be performed within initial treatment by using the minimization method^{62,63} to achieve study-wide balance across treatments. Over the course of the study, the number and proportion of participants assigned to augmentation and switching overall, blinded to initial treatment assignment, will be monitored. If the proportions in each group differ meaningfully from the underlying assumptions used in the estimation of sample size, the proportion randomized to augment vs switch within Group 3 will be adapted to maintain power.

All Potential Second Stage All Potential Sw		All Potential Switches to Second
First Stage Treatment	Augmentations	Treatments
ESC	ESC + ACT	N/A
	ESC + Duloxetine	
	ESC + EBEM	
ACT	ESC + ACT	ESC
	ACT + Duloxetine	Duloxetine
	ACT + EBEM	EBEM
Duloxetine	ESC + Duloxetine	ESC
	ACT + Duloxetine	ACT

	Duloxetine + EBEM	EBEM
EBEM	ESC + EBEM	ESC
	ACT + EBEM	ACT
	Duloxetine + EBEM	Duloxetine

Participants who must discontinue first-stage treatment early, regardless of their PGIC or PEG score, will be randomized to switch to a second treatment. These individuals will discontinue treatment and will be randomized to switch to a second-line treatment 12 weeks post baseline (Visit 1).

Randomization will be performed using the Carolina Data Acquisition and Reporting Tool (CDART), developed by the Collaborative Studies Coordinating Center at the University of North Carolina. CDART is designed and implemented as a centrally hosted, web-based, customizable and scalable data management system. Randomization algorithms will be developed by a biostatistician and custom-written in Java, which provides a full set of libraries and tools capable of complex algorithm implementation. This data management system will provide a means for implementing treatment allocation protocols, masking allocation of future participants, and for study staff to obtain allocation information immediately following randomization. Study staff and participants will not be blinded to treatment allocation given the nature of the interventions. Study investigators and staff involved in data analysis will be blinded to assignment.

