- Previous reports of similar AEs associated with the study agent or other agents in the same class, and
- Recurrence of the AE after re-challenge or resolution after de-challenge, if applicable.

Further assessment of causality is provided by the DSMB based on accumulating safety reports between treatment groups.

The terms used to assess the relationship of an event to study agent are:

- Related There is a reasonable possibility that the AE may be related to the study agent(s).
- Not Related There is not a reasonable possibility that the AE is related to the study agent(s).

Expectedness

Expected AEs are AEs that have been previously observed with the study intervention or procedures. An adverse event is considered "unexpected" if its nature, severity, or frequency is **not** consistent with either of the following:

- the known or foreseeable risk of adverse events associated with the procedures involved in the research that are described in (a) the protocol-related documents, such as the IRB-approved research protocol, any applicable investigator brochure, and the current IRB-approved informed consent document, and (b) other relevant sources of information, such as product labeling and package inserts; or
- the expected natural progression of any underlying disease, disorder, or condition of the subject(s) experiencing the adverse event and the subject's predisposing risk factor profile for the adverse event.

12.3.4.TIME PERIOD AND FREQUENCY FOR EVENT ASSESSMENT AND FOLLOW-UP

The occurrence of an adverse event (AE) or serious adverse event (SAE) may come to the attention of study personnel during study visits and interviews of a study participant presenting for medical care, or upon review by a study monitor.

All AEs including local and systemic reactions not meeting the criteria for SAEs will be captured on the appropriate case report form (CRF). Information to be collected includes event description, time of onset, clinician's assessment of severity, relationship to study intervention (assessed only by those with the training and authority to make a diagnosis), and time of resolution/stabilization of the event. All AEs must be documented appropriately regardless of relationship. All AEs will be followed to adequate resolution.

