We expect missing data to be minimal because of study procedures discussed previously to enhance retention such as incentives, incorporation of patient stakeholder feedback in the development of study materials, and efforts to minimize participant burden. In addition, there will be ongoing participant engagement through a study website, contact with research staff and regular patient engagement efforts. Finally, protocols for discontinuation of study treatment that are not tolerated are planned to enhance retention. We will continue to follow all participants until the end of the study and will utilize alternative forms of data collection for those who do not attend planned study visits (e.g., telephone administration or online data collection). Despite these efforts, missing data will arise and, as needed and appropriate, will be addressed using non-parametric multiple imputation procedures. Sensitivity analyses will be presented in detail as part of the SAP.

13.4.2.ANALYSIS OF THE PRIMARY EFFICACY ENDPOINT(S)

Complete details will be provided in the formal Statistical Analysis Plan for the study.

13.4.3.ANALYSIS OF THE SECONDARY ENDPOINT(S)

Complete details will be provided in the formal Statistical Analysis Plan for the study.

13.4.4.SAFETY ANALYSES

No safety analyses are planned other than descriptive summaries and data listings of reported adverse events.

13.4.5.BASELINE DESCRIPTIVE STATISTICS

Complete details will be provided in the formal Statistical Analysis Plan for the study.

13.4.6.PLANNED INTERIM ANALYSES

No interim analyses are planned for the study. Adaptation to the design, *i.e.* the second stage randomization probabilities, is planned and details will be included in a future Statistical Analysis Plan. Briefly, overall proportions of participants assigned to augment or switch will be monitored. If proportions deviate meaningfully from assumptions, we will consider shifting randomization probabilities within Group 3 (*e.g.*, from 50/50 to 60/40 augment/switch).

13.4.7.SUB-GROUP ANALYSES

N/A

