14.1.12. DATA COLLECTION AND MANAGEMENT RESPONSIBILITIES

Data collection is the responsibility of the study staff at the site under the supervision of the site investigator. The investigator is responsible for ensuring the accuracy, completeness, legibility, and timeliness of the data reported.

All source documents should be completed in a neat, legible manner to ensure accurate interpretation of data.

Data recorded in the electronic case report form (eCRF) derived from source documents should be consistent with the data recorded on the source documents.

Adverse events will be coded using the Medical Dictionary for Regulatory Activities (MEDDRA) and concomitant medications will be coded using the National Drug Code (NDC) Directory.

Clinical data (including adverse events (AEs), concomitant medications, and expected adverse reactions data) and clinical laboratory data will be entered into CDART, a 21 CFR Part 11-compliant data capture system managed by the DAC. The data system includes password protection and internal quality checks, such as automatic range checks, to identify data that appear inconsistent, incomplete, or inaccurate. Clinical data will be entered directly from the source documents.

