### **Additional Analyses**

Additional reporting is included in this submission for adverse events (Appendix 3)

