# Appendix 3 Table 3: Clinical Trials Adverse Event Reporting Table Other (Not Including Serious) Adverse Events Over a Threshold of 5%

Population: All Participants Randomized to Stage 1 (N=805); Including All Participants Randomized to Stage 2 (N=683)

	/ Threshold ing Other Events	5%							
System Organ Class	Preferred Term	Stage 1 ACT (N=xx)		Stage 1 Duloxetine (N=xx)		Stage 1 EBEM (N=xx)		Stage 1 ESC (N=xx)	
		Affected / at Risk (%)	# Events	Affected / at Risk (%)	# Events	Affected / at Risk (%)	# Events	Affected / at Risk (%)	# Events
	Total	x/N (x.x%)	у	x/N (x.x%)	У	x/N (x.x%)	У	x/N (x.x%)	
System Organ Class A	Preferred Term A1	x/N (x.x%)	у	x/N (x.x%)	у	x/N (x.x%)	У	x/N (x.x%)	У
System Organ Class A	Preferred Term A2	x/N (x.x%)	У	x/N (x.x%)	у	x/N (x.x%)	У	x/N (x.x%)	У
System Organ Class B	Preferred Term B1	x/N (x.x%)	У	x/N (x.x%)	У	x/N (x.x%)	У	x/N (x.x%)	У
System Organ Class B	Preferred Term B2	x/N (x.x%)	у	x/N (x.x%)	у	x/N (x.x%)	У	x/N (x.x%)	У

Othe	r (Not Inclu	ıding Serious)	Adverse E	vents					
Frequent Threshol Reportin Adverse	ld for g Other	5%							
	Preferred Term	Stage 2 ACT (N=xx)		Stage 2 Duloxetine (N=xx)		Stage 2 EBEM (N=xx)		Stage 2 ESC (N=xx)	
		Affected / at Risk (%)	# Events	Affected / at Risk (%)	# Events	Affected / at Risk (%)	# Events	Affected / at Risk (%)	# Events
	Total	x/N (x.x%)	у	x/N (x.x%)	у	x/N (x.x%)	У	x/N (x.x%)	
System Organ Class A	Preferred Term A1	x/N (x.x%)	У	x/N (x.x%)	у	x/N (x.x%)	У	x/N (x.x%)	у
System	Preferred Term A2	x/N (x.x%)	у	x/N (x.x%)	у	x/N (x.x%)	У	x/N (x.x%)	У
System Organ Class B	Preferred Term B1	x/N (x.x%)	у	x/N (x.x%)	У	x/N (x.x%)	у	x/N (x.x%)	У
System Organ Class B	Preferred Term B2	x/N (x.x%)	у	x/N (x.x%)	У	x/N (x.x%)	у	x/N (x.x%)	У

Othe	r (Not Inclu	ıding Serious)	Adverse E	vents					
Frequent Threshol Reportin Adverse	ld for g Other	5%							
	Preferred Term	Stage 2 ACT and Duloxetine (N=xx)		Stage 2 ACT and EBEM (N=xx)		Stage 2 ACT and ESC (N=xx)		Stage 2 Duloxetine and EBEM (N=xx)	
		Affected / at Risk (%)	# Events	Affected / at Risk (%)	# Events	Affected / at Risk (%)	# Events	Affected / at Risk (%)	# Events
	Total	x/N (x.x%)	у	x/N (x.x%)	У	x/N (x.x%)	У	x/N (x.x%)	
_	Preferred Term A1	x/N (x.x%)	У	x/N (x.x%)	У	x/N (x.x%)	У	x/N (x.x%)	у
System	Preferred Term A2	x/N (x.x%)	У	x/N (x.x%)	у	x/N (x.x%)	У	x/N (x.x%)	У
	Preferred Term B1	x/N (x.x%)	У	x/N (x.x%)	У	x/N (x.x%)	У	x/N (x.x%)	У
-	Preferred Term B2	x/N (x.x%)	у	x/N (x.x%)	У	x/N (x.x%)	у	x/N (x.x%)	У

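### The SAP's only table of non-serious adverse events names just the preferred terms above 5% and omits severity and relationship, so infrequent terms go unnamed in its outputs

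*SAP*

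**What the plan says.** Reporting adverse events is one of the SAP's stated aims (SAP, Objectives). For the outputs, its text says only this: "Additional reporting is included in this submission for adverse events (Appendix 3"). Appendix 3 has three tables: all-cause mortality (Table 1), serious adverse events (Table 2, no frequency cut), and Table 3, headed "Other (Not Including Serious) Adverse Events Over a Threshold of 5"%.

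Table 3 has 14 treatment columns, four for Stage 1 and ten for Stage 2. Each gives the number and percentage affected and the event count, by system organ class and preferred term. The SAP does not say whether the 5% is judged in each column, in any column, or over the whole population.

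The protocol is broader:

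- Section 13.4.4: "No safety analyses are planned other than descriptive summaries and data listings of reported adverse events". No frequency cut is mentioned.
- Section 12.3.4 requires the case report form to capture the clinician's "assessment of severity, relationship to study intervention (assessed only by those with the training and authority to make a diagnosis").
- Section 14.1.12: "Adverse events will be coded using the Medical Dictionary for Regulatory Activities (MEDDRA").
- Section 5.2.1: "The most serious adverse effect associated with duloxetine is the increased risk of suicidality with initiation, especially in individuals under age 25".
- Section 5.2.3: "Participants on duloxetine will be monitored appropriately for clinical worsening, suicidality, or unusual changes in behavior".

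**The concern.** A 5% cut keeps a results table short, but here it governs the only table that covers non-serious events. Any term below the cut is not named anywhere in the SAP's outputs. For the terms that are named, the reader cannot tell mild from severe or related from unrelated, although every site has to record this.

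Duloxetine is the natural test case. The protocol names one gravest risk for it. Some such events would meet the serious criteria and appear in Table 2. Others could be classed as non-serious, and at a low rate these could fall below the cut. What is at stake is the completeness of the published safety account of the trial's one drug arm. No efficacy estimate or decision rule is involved.

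**Working it through.** **Inputs.** Stage 1 arms (SAP Appendix 2 table): 203 + 198 + 199 + 205 = 805, which matches the SAP's randomised total. Stage 2 total: 683 (Appendix 3). The documents give neither an event rate nor the Stage 2 column sizes. True rates of p = 1% and 2%, and a range of column sizes, are assumed below.

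**Count needed.** A column of n participants exceeds 5% at the smallest r with r/n > 0.05.

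- n = 198: 0.05 × 198 = 9.9, so r = 10 (10/198 = 5.05%; 9/198 = 4.5%).
- n = 805: 0.05 × 805 = 40.25, so r = 41 (41/805 = 5.09%).

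**Rule (a): cut applied to the Stage 1 duloxetine column.** With X ~ Binomial(198, p):

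| | p = 1% | p = 2% |
|---|---|---|
| Expected cases, 198p | 1.98 | 3.96 |
| At least one case, 1 − (1 − p)^198 | 86.3% | 98.2% |
| Term named, P(X ≥ 10) | 0.004% | 0.7% |

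At least one case is likely, and naming the term is very unlikely.

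**Rule (b): cut pooled over 805.** This needs 41 participants. If all came from the Stage 1 duloxetine arm, that would be 41/198 = 20.7% of it. Even at 2% in all 805 participants the chance is about 1 in 10 million.

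**Rule (c): above 5% in any column.** Five columns contain duloxetine: Stage 1 duloxetine, and in Stage 2 duloxetine alone or with ACT, EBEM or ESC. Treating columns as independent, with four equal Stage 2 columns of size n:

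P(named) = 1 − (1 − P₁₉₈)(1 − Pₙ)⁴

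where P₁₉₈ and Pₙ are the chances that a column of that size exceeds 5%.

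| n per Stage 2 column | Cases needed | p = 1% | p = 2% |
|---|---|---|---|
| 19 | 1 | 53% | 79% |
| 39 | 2 | 21% | 56% |
| 40 | 3 | 3.0% | 18% |
| 59 | 3 | 8.3% | 39% |
| 68 (683/10) | 4 | 2.0% | 18% |
| 100 | 6 | 0.2% | 6.7% |

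Over every n from 40 to 100 the ranges are 0.2–8% and 7–39%. The chance jumps where the required count changes. At 2% it is above 50% for all sizes from 36 to 39, and again below 20, where a single case is enough.

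Equal columns are not what the design produces, because "Patients initially randomized to ESC with 12-week PGIC scores of 3-7 will be randomized to augmentation and not switching", which enlarges the combinations with ESC. I therefore built columns from assumed response shares:

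- 683/805 of each Stage 1 arm goes on to Stage 2.
- 10–30% maintain, 5–20% are in Group 2 and 10–40% in Group 4, in 5-point steps.
- The rest, at least 10%, are in Group 3 and split 50/50 between augmenting and switching.
- The three available treatments are equally likely.

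This gives 140 scenarios with duloxetine columns of 20 to 110. P(named) is 2–12% at 1% and 17–41% at 2%. In a wider grid of 364 scenarios (maintain 5–40%, Group 2 5–30%, Group 4 5–40%), three exceed 50% at 2%, with a maximum of 55%. Each of those three has a duloxetine column below 20.

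**Sensitivity to the rate.** At 3% and 4%, rule (a) gives 7.7% and 27%. Rule (c), with equal columns of 40–100, gives 34–72% and 72–92%.

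**The case against.** **Table 3 is a registry format, and Tables 1–3 are themselves descriptive summaries.** This stands. Only the protocol's listing has no counterpart in the SAP, and the protocol does not promise tabulation by severity or relationship. Adding those columns is an improvement on the plan and repairs no broken commitment.

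**The listing remains planned.** A reader might infer that the SAP has dropped the protocol's listings. The documents do not support that: the SAP is silent and withdraws nothing. It also limits itself to one outcome analysis and places even the trial's primary estimand outside its scope.

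**Suicidality would be serious.** Some of it would be. Important medical events count as serious (protocol 12.3.2), and Table 2 has no threshold. That criterion is a judgement, and the protocol does not make ideation serious automatically, so a non-serious remainder is possible. Its size is unknown. Participants with a history of suicide attempts, bipolar disorder or manic episodes cannot be assigned duloxetine (8.3), which may lower it.

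**The probabilities rest on assumptions.** A reader might infer that a suicidality term would probably be hidden whichever way the cut is applied. That goes too far. Under the any-column rule the chance of naming it passes 50% at a 2% rate for some column sizes, and rises further at 3–4%. The calculation also uses one constant rate, although the protocol ties the risk to initiation and the Stage 2 columns mix new starters with continuers. It treats columns as independent, although the same people can appear in both stages.

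**Oversight is intact.** This stands. The DSMB receives serious and non-serious events by treatment group (14.1.8).

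**Conclusion.** The concern holds in a limited form. Table 3 is the SAP's only output for non-serious events. It drops terms at or below 5% and shows neither severity nor relationship, so infrequent non-serious terms are missing by name from the SAP's outputs. This rests on the text alone.

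The duloxetine figures are an illustration. If the cut is applied to the Stage 1 duloxetine column, a non-serious term at an assumed 1–2% would almost certainly not be named there. Under an any-column rule no firm statement is possible without the Stage 2 sizes and the rate. For severe events in general no probability is claimed: a severe case of a common term is named through its milder cases, and what is lost is the severity.

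The consequence is confined to reported results. The unstated basis of the 5% and the absence of the listing from the SAP are missing details and would not carry the point alone. What carries it is a stated cut that removes information the trial already collects.

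**What to change.** Keep Table 3 as it is for the registry. Add to Appendix 3 one table of all non-serious adverse events by system organ class and preferred term, with no frequency threshold, showing severity (mild, moderate, severe) and relationship (related, not related) in the same treatment columns. In the same edit, say how the 5% in Table 3 is applied and refer to the protocol's listing.

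This is a cheap improvement: some SAP wording and one table from data already collected and MedDRA-coded. The downside is a longer output with many sparse cells.

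A separate duloxetine row for suicidality-related terms is optional, because the unthresholded table would already name them. If it is wanted, the MedDRA term list should be fixed in advance. The row would rest on adverse event reports only, since the questionnaires in protocol section 16 include no dedicated suicidality instrument.

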Description of Sites/Facilities Enrolling Participants: Approximately 12 U.S. sites will enroll participants into BEST; all sites are clinic settings.

Description of Study Interventions:

Acceptance Commitment Therapy

ACT is a form of cognitive behavioral therapy that is well established for the treatment of chronic pain⁷⁻¹². The goal of ACT is to build psychological flexibility thereby interrupting pain avoidance behavior patterns. Participants randomized to ACT will take part in 12 sessions over the course of 12 weeks. Sessions will be delivered as a combination of 4 remote face-to-face visits with a therapist and 8 therapist-supported online sessions (self-directed online modules supported by provider coaching). Online sessions will focus on helping participants accept pain, connect with negative thoughts and emotions, develop mindfulness and identify and commit to values and goals that are important to them. During face-to-face sessions with the therapist, participants will be

encouraged to share their experience of skills practice and mastery, provide examples of skill use at home, and describe what barriers they encountered.

Duloxetine

Duloxetine is a serotonin norepinephrine reuptake inhibitor (SNRI) that is FDA-approved for use in cLBP¹³, and, as such, is included as a recommended therapy in nearly all current treatment guidelines for low back pain. Study participants will be treated with duloxetine for 12 weeks during the active treatment phase. At the time of randomization, the approved drug pharmacy at each study site will dispense between 185 and 192 duloxetine 30 mg capsules and provide to participants. This will ensure enough capsules to maintain up to a 60 mg dosage through the 12-week intervention phase. A standard tapering period will occur in the 13th and 14th weeks, as needed. At the investigator or licensed designee's discretion, tapering can be extended up to the 15th week.

Enhanced Self-Care

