or Week 18 calls. For participants who are taking 60mg daily, they will be instructed to reduce their dosage to 30mg per day for one week, and reduce to 30mg every other day for a week, as needed to reduce mild side effects. Participants taking 30mg per day can reduce their dosage to 30 mg every other day for up to 2 weeks, as needed to reduce mild side effects. At the discretion of the site PI or licensed designee, tapering can be extended an additional week, with the last dose no later than 21 days after Visit 1 or 2.

10.2.2.ACQUISITION AND ACCOUNTABILITY

Site staff will be responsible for ensuring study participants are instructed on how to return study medications and for tracking returned medication.

When medication is returned, site staff will count how many capsules are left and this number will be reported on the drug accountability log, and the remaining capsules will be disposed according to local, institutional policy.

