#### Trial/Study Design

Study data for this analysis will be from the BEST Trial, which has been described elsewhere. The trial follows a two stage sequential multiple assignment random trial SMART trial plan. The trial is split into two 12-week intervention stages with 3 study visits that occurred at the beginning of Stage 1 (Visit 0/Week 0), Stage 2 (Visit 1/Week 12), and the end of Stage 2(Visit 2/Week 24). At baseline (Visit 0/Week 0) participants were randomized to one of four interventions. To participate in the study participants were required to be eligible for a minimum of 3 of the treatments at baseline. A re-randomization happened at Week 12, where participants were assigned to one of four responder status categories using a combination of Week 12 Pain, Enjoyment of Life, and General Activity (PEG) and Patient Global Impression of Change (PGIC) scores. Participants with Week 12 PGIC 1-2 and PEG <= 4 maintained their initial treatment, participant with Week 12 PGIC 1-2 and PEG > 4 were randomized to augment a second treatment, participants with a Week 12 PGIC 3-4 were randomized to either augment a second treatment or switch treatments, and participants with a Week 12 PGIC of 5-7 or participants who could not tolerate their initial treatment were switched to a new treatment. Randomization at the baseline visit was stratified by years of cLBP, depression/anxiety, consent to optional phenotyping, and current use of opioids. The details of the trial are illustrated in the schema below.

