#### **Analysis Populations**

The population used for statistical analysis consists of the 805 randomized participants to a Stage 1 treatment.

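### The Stage 2 adverse event tables have no place for events during the duloxetine taper, and they pool participants starting duloxetine with those continuing it

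*SAP*

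**What the plan says.** **Table layout.** SAP Appendix 3 holds three shells: all-cause mortality, serious events, and other events above 5%. Each covers "Population: All Participants Randomized to Stage 1 (N=805); Including All Participants Randomized to Stage 2 (N=683"). There are four Stage 1 columns and ten Stage 2 columns. The ten are the four single treatments, for example "Stage 2 Duloxetine (N=xx"), and the six pairs. None is defined by the Stage 1 treatment. The SAP's only text on how adverse events will be reported, under Additional Analyses, points to this appendix. Neither document gives a lag window, a treatment-emergent definition or a rule for assigning an event to a stage.

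**Timing.** The SAP's Trial/Study Design section says "The trial is split into two 12-week intervention stages with 3 study visits" and starts Stage 2 at Visit 1 (Week 12). The protocol synopsis says of duloxetine that "A standard tapering period will occur in the 13th and 14th weeks, as needed", and that at the investigator's discretion "tapering can be extended up to the 15th week". Protocol Section 10.2.1 agrees: "tapering can be extended an additional week, with the last dose no later than 21 days after Visit 1 or 2". Under Section 12.3.4, events are recorded until 4 weeks after the last treatment, so events during the taper are collected.

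**Starting versus continuing.** Protocol Section 5.2.1 links the most serious duloxetine risk to initiation and says that many side effects ease with time. Sections 10.2.1 and 12.2 give an extra safety call on day 7 only to participants newly randomized to the drug, in either period.

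**Sequences.** The SAP's flow table lists duloxetine followed by ACT, duloxetine plus ACT, and ACT plus duloxetine as separate arms. The adverse event tables do not.

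**The concern.** Two different mixtures arise.

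- **Carry-over.** A participant switched from duloxetine to ACT, EBEM or ESC at Visit 1 may still be taking the drug, or coming off it, early in Stage 2. The taper is there to limit mild side effects, so the protocol itself expects some in that window. If the shells are filled in as drawn, such an event has no Stage 2 column except that of a non-drug treatment.
- **Pooling.** Stage 2 Duloxetine combines participants maintained on the drug after 12 weeks with participants newly switched to it from ACT or EBEM. Each of the three duloxetine pairs combines duloxetine added to a partner with a partner added to duloxetine. By the protocol's account these groups differ in risk, and through the day-7 call they also differ in how closely events are sought.

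At stake is how the safety tables read. Adverse event reporting is a stated SAP aim, and Protocol Section 13.4.4 plans nothing beyond descriptive summaries and listings, so no later analysis would separate the groups.

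**Working it through.** **Step 1: the plan's own figures.** The baseline shell gives ACT 203, duloxetine 198, EBEM 199 and ESC 205. The sum is 203 + 198 + 199 + 205 = 805, which matches the stated Stage 1 total. Stage 2 has 683, so 805 - 683 = 122 were not re-randomized and retention is 683/805 = 84.8%. The documents do not break 683 down by sequence, so everything from Step 3 on rests on assumed shares.

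**Step 2: length of the overlap.** Stage 2 lasts 12 x 7 = 84 days. The longest taper is 21 days, 21/84 = 25% of the stage, ending at week 12 + 3 = 15, in line with the synopsis. The standard taper is 14/84 = 17%.

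**Step 3: assumptions.** Retention is 683/805 in every arm. That leaves about 172 from ACT, 168 from duloxetine, 169 from EBEM and 174 from ESC. A share *m* of 20-30% maintains and a share *s* of 30-50% switches, alike in the three arms that can switch. ESC starters maintain at *m* and never switch. The other options are equally likely. The rest, 1 - *m* - *s*, augment.

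**Step 4: former duloxetine participants in the non-drug columns.** The number leaving duloxetine is 168*s*, or 50 to 84, which is 17 to 28 for each new treatment.

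| Stage 2 column | Column size | Lowest (*m* = 0.3, *s* = 0.3) | Highest (*m* = 0.2, *s* = 0.5) |
|---|---|---|---|
| ACT | 172*m* + (168 + 169)*s*/3 | 17/85 = 20% | 28/91 = 31% |
| EBEM | 169*m* + (172 + 168)*s*/3 | 17/85 = 20% | 28/90 = 31% |
| ESC | 174*m* + (172 + 168 + 169)*s*/3 | 17/103 = 16% | 28/120 = 23% |

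**Step 5: convert headcount to time.** If every one of them tapered for all 21 days, taper would be 0.25 x 20-31% = about 5-8% of person-time in the ACT and EBEM columns. At 14 days it is 0.17 x 20-31% = about 3-5%. Both are ceilings, because tapering is as needed.

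**Step 6: continuers in the duloxetine columns.** In Stage 2 Duloxetine the continuers' share is 168*m* / [168*m* + (172 + 169)*s*/3].

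- *m* = 0.2, *s* = 0.5: 34/90 = 37%.
- *m* = 0.3, *s* = 0.3: 50/84 = 60%.

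In ACT and Duloxetine, new starters are 172/(172 + 168) = about 51%. In Duloxetine and EBEM they are 169/(169 + 168) = about 50%. In Duloxetine and ESC they are 174(1 - *m*) / [174(1 - *m*) + 168(1 - *m* - *s*)]. This runs from 139/(139 + 84) = 62% at *m* = 0.2, *s* = 0.3 to 122/(122 + 34) = 78% at *m* = 0.3, *s* = 0.5.

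**Step 7: what pooling could do to a rate.** As an illustration with rates that are not in the documents, take an event in 30% of starters and 10% of continuers. At 37% continuers the pooled column reads 0.63 x 30% + 0.37 x 10% = 23%. At 60% it reads 0.40 x 30% + 0.60 x 10% = 18%.

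**The case against.** Grouping by current treatment is an ordinary choice for descriptive tables, and several stronger readings go beyond the documents.

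- **That the tables will misattribute taper events.** The SAP never says where such events go. It follows from the columns and the absence of a rule, so the tables *can* overstate or understate; they are not shown to do so.
- **That 20-31% of the ACT and EBEM columns is contaminated.** This is a headcount. The 21-day limit needs clinical discretion, the time share is at most about 5-8%, and no event rate during the taper is given.
- **That everyone switched off duloxetine carries it into Stage 2.** Protocol Section 10.4.4 also sends to a switch those who had to stop first-stage treatment early. They would normally be off the drug before Visit 1, which lowers the true carry-over further.
- **That the start-up profile of duloxetine is lost.** Current duloxetine use bars randomization to the drug (Section 8.3), so the Stage 1 Duloxetine column (198 participants) consists of new starters. What is blurred is starting in Stage 2, most of all on top of another treatment.
- **That common events will drop below the 5% threshold.** An event in 8% of starters and 1% of continuers, mixed equally, gives 4.5%. It goes unreported only if the threshold is applied column by column, which the SAP does not say. If a term is listed whenever any column passes 5%, Stage 1 Duloxetine could still bring it in. The threshold does not apply to the mortality and serious event tables.
- **That these tables are the only safety record.** Listings are planned too, and the monitoring board reviews safety data by treatment.

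All of this limits the size of the point. It does not remove it: the published columns would still merge groups that the protocol treats as different and that the flow table already separates.

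**Conclusion.** The point holds for the layout of the Stage 2 safety tables. They give no place to events during the duloxetine taper other than a non-drug column, and they pool starters with continuers in four columns. The likely direction is too many events for ACT, EBEM and ESC and too few for starting duloxetine in Stage 2.

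The pooling is the larger part: about 37-60% continuers in Stage 2 Duloxetine, and new starters from about half to 78% of the three pairs. The carry-over is smaller, at most about 5-8% of person-time in ACT and EBEM. All these figures depend on equal retention across arms, the assumed maintain and switch shares, and equally likely options. The effect on event rates cannot be computed from the documents. The tables are descriptive and no test or primary result depends on them, so this is a worthwhile improvement and not a threat to the trial's conclusions.

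**What to change.** In SAP Appendix 3:

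1. For participants switched off duloxetine at Visit 1, report events from Visit 1 to the end of the taper in a separate duloxetine taper category instead of under the new treatment. State the at-risk number (those who took the drug after Visit 1). The documents do not say whether the date of the last taper dose is recorded. If it is not, use the protocol's 21-day limit as the reporting window. Add a footnote that the new treatment may already have begun in this window.
2. Break the four Stage 2 columns containing duloxetine into started in Stage 2 and continued from Stage 1, as sub-columns or in a supplementary table, and keep the pooled column. Footnote that only starters had the day-7 call.

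Do not also split ACT, EBEM and ESC by prior duloxetine. With the four duloxetine splits that would make 10 + 4 + 3 = 17 columns averaging 683/17 = about 40 people. The former duloxetine group in Stage 2 ACT would be 17-28 people, so a single event would be 1/28 to 1/17, or 3.6-5.9%. Noise would replace dilution.

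The cost is a change of table shell, using the two assignments already held, and a few smaller columns. If the three tables must keep their present form for submission, the supplementary table carries the breakdown. No change to the taper itself is implied.
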